## 11. Hemodynamic management

- a. We will recommend continuous monitoring of MAP in both the study arms.
- b. We will recommend withholding of UFNET in both arms for hypotensive episodes as determined by bedside clinicians.
- c. We will recommend titration of vasopressors by bedside clinicians, as needed, during fluid removal for hemodynamic management.

## 12. CKRT management

- a. We will protocolize solute clearance with an effluent flow rate of 20-30 mL/kg/h.
- b. We will recommend CKRT modality, hemofilter, blood flow rate, dialysate use, dialysate flow rate, buffers, pre- and post-filter substitution fluids, and anticoagulation as determined by attending nephrologist.
- c. We will recommend that CKRT machine is functioning at least 20 hours a day.
- d. We will recommend CKRT circuit change every 48-72 hours.

## 13. Other care

- a. We will provide recommendations for conservative fluid management in both study arms.
- b. We will provide criteria for initiation of rapid rescue net ultrafiltration.

### **Inclusion Criteria**

1. Age  $\geq$ 18 years
2. Stage 3 acute kidney injury according to the KDIGO criteria
3. Started or intending to start CKRT for volume management
4. Attending intensivist or nephrologist intending to remove net fluid using CKRT for at least 48 hours

### **Exclusion Criteria**

1. Respiratory distress due to pulmonary edema or fluid overload in un-intubated patients
2. Massive volume infusion (*i.e.*, >200 mL/h for >6 hours of continuous infusion)
3. No intention to remove net fluid as determined by attending intensivist or nephrologist
4. Attending intensivist or nephrologist believes that the protocol will not be followed
5. Continuous net fluid removal for >48 hours prior to study enrollment
6. Patients on chronic outpatient hemodialysis
7. Patients with history of, or current admission for kidney transplantation
8. Patients on comfort measures only orders (*i.e.*, CMO)
9. Moribund not expected to survive >24 hours
10. Confirmed pregnancy
11. Patients treated with extracorporeal membrane oxygenation (ECMO), ventricular assist device (VAD), or intra-aortic balloon pump (IABP)
12. Organ donors with neurological determination of death (*i.e.*, brain dead donors)
13. Drug overdose requiring CKRT for drug clearance

14. Enrollment in a concurrent interventional clinical trial with direct impact on fluid balance (e.g., >500 mL study drug administration)

**Assessing Attending Physician Equipoise:** After meeting inclusion and none of the exclusion criteria, the attending intensivist or nephrologist will be asked twice daily if she/he strongly believed:

- a) emergent and rapid fluid removal should occur

OR

- b) fluid removal should be defered

If the answer is negative to both questions, the patient will be considered fully eligible and efforts to obtain informed consent from patient or LAR will commence. If a patient's eligibility is excluded by an attending physician, the patient will be reconsidered for participation in the trial, and the physician will be re-approached later, provided the patient still meets inclusion criteria and none of exclusion criteria.

**Study Initiation Time Window:** All patients must be consented and enrolled within 48 hours of meeting full eligibility. Time of signing the informed consent will be the study enrollment time. Once enrolled, the assigned intervention must be initiated within 24 hours.

**Discontinuation of Study Protocol:** The study protocol will be continued until one of the following occurs:

1. Attending intensivist or nephrologist determines that fluid removal is no longer necessary using CKRT.
2. Attending intensivist or nephrologist decides to stop CKRT and transition the patient to IHD.
3. The patient or surrogate decision-makers decide to withdraw life-sustaining treatment.
4. The patient dies.
5. Day 28 after study enrollment, whichever occurs first.

**Primary Outcomes:** The primary feasibility outcomes are as follows:

1. Between-group separation in mean delivered UFNET rates of a minimum of 0.53 mL/kg/h.
2. Protocol deviation defined as UFNET rate out of range of >0.5 mL/kg/h lower or higher than the assigned UFNET rate range for six consecutive hours.
3. Patient recruitment of one patient per time window per ICU.

## **Secondary Outcomes**

1. Daily fluid balance
2. Cumulative fluid balance
3. Duration of kidney replacement therapy
4. Duration of mechanical ventilation

5. Organ failure free days
6. ICU length of stay
7. Hospital length of stay
8. Hospital mortality
9. Dialysis dependence at hospital discharge

### **Safety Outcomes**

1. Intradialytic hypotensive episodes
2. Intradialytic hypertensive episodes
3. Intradialytic new onset cardiac arrhythmias including supraventricular tachycardia, bradycardia, atrial fibrillation, ventricular tachycardia, ventricular fibrillation, and cardiac arrest
4. Emergent use of rescue UFNET with rates higher than the assigned treatment arm
5. Severe hypophosphatemia (<0.5 mg/dL)
6. Severe hypokalemia (<3.0 mg/dL)
7. Severe hypocalcemia (<1.90 mg/dL or ionized calcium <0.90 mmol/L)
8. CKRT system downtime due to filter clotting or clogging
9. Discontinuation of UFNET due to hemodynamic instability
10. Inability to close surgical wounds due to edema
11. New organ dysfunction
12. Worsening of systolic or diastolic cardiac function on echocardiogram
13. Worsening of pulmonary edema on chest X Ray and/or CT scan
14. Worsening of ileus on abdominal X Ray and/or CT scan
15. Bowel ischemia or anastomotic breakdown based on intraoperative findings
16. Pressure ulcerations
17. New wound infections
18. New arterial or venous thrombosis
19. Severe anemia requiring red cell transfusions
20. Severe thrombocytopenia requiring platelet transfusions
21. New secondary infections

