### **Sample Size/Interim Monitoring**

[figure not shown]
1. Using the sample size calculation for SW-CRT design, 111 patients will have 80% power at a two-sided alpha of 0.05 to reject the null hypothesis that the average UFNET rate was at least 0.53 mL/kg/h different between the two groups, using intra-cluster correlation coefficient of 0.01, at a standard deviation of 0.75, and assuming mean UFNET rate of 1.0 mL/kg/h. We will enroll 112 subjects or 56 patients per group.
2. The principal analysis will be intent-to-treat based upon randomization assignment.
3. The trial progress will be evaluated by an independent Data and Safety Monitoring Board (DSMB). Being a feasibility study there will be no interim analyses.

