#### *5.2.2.5 Severe hypokalemia, hypophosphatemia and hypocalcemia*

Severe hypophosphatemia will be defined as intradialytic phosphate level  $<0.5$  mg/dL. Severe hypokalemia is defined as a intradialytic potassium level  $<3.0$  mg/dL. Severe hypocalcemia will be defined as intradialytic serum calcium level  $<1.90$  mg/dL or ionized calcium  $<0.90$  mmol/L.

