5.3.3 TABLE 3: SAFETY OUTCOMES

Safety Outcomes	Restrictive		Liberal		Unadjusted P value	Adjusted P value §
	No. of Patients (%)	No. of episodes	No. of Patients (%)	No. of episodes		
Intradialytic hypotension						
Intradialytic hypertension						
Cardiac arrhythmias						
Use of rescue net ultrafiltration						
Hypophosphatemia (<0.5 mg/dL)						
Hypokalemia (<3.0 mg/dL)						
Hypocalcemia (<1.90 mg/dL)						
Hemofilter clotting or clogging						
UF NET discontinuation due to instability						
Surgical wounds edema						
New organ dysfunction						
Worsening cardiac function						
Worsening of pulmonary edema						
Worsening of ileus						
Bowel ischemia or anastomotic breakdown						
New pressure ulcerations						
New wound infections						
New arterial or venous thrombosis						
Severe anemia						
Severe thrombocytopenia						
New secondary infections						

§ Adjusted for differences in age, baseline eGFR, APACHE-III score, Elixhauser Comorbidity Index score, mechanical ventilation, admission source, percentage of fluid overload, sepsis, and baseline cardiovascular SOFA score. P values are for the between-group differences in the percentage of patients with a specific event and have not been adjusted for multiple comparisons.

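### The severe hypokalemia threshold and the total-calcium limb of severe hypocalcemia carry implausible units in both documents: taken literally, hypokalemia would count about zero events and hypocalcemia would rest on ionized calcium alone.

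*Protocol*

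**What the plan says.** Protocol section 4 (Safety Outcomes) lists "Severe hypokalemia (<3.0 mg/dL") with no alternative criterion, and "Severe hypocalcemia (<1.90 mg/dL or ionized calcium <0.90 mmol/L"), which is two criteria joined by an or. Section 5.8.3 of the protocol and section 3.5.3 of the SAP give the same limits.

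SAP section 5.2.2.5 is the derivation a programmer would follow. It reads "Severe hypokalemia is defined as a intradialytic potassium level" below 3.0 mg/dL. For calcium it reads "Severe hypocalcemia will be defined as intradialytic serum calcium level" below 1.90 mg/dL, or ionized calcium below 0.90 mmol/L.

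Shell Table 3 (SAP 5.3.3) labels the rows "Hypokalemia (<3.0 mg/dL") and "Hypocalcemia (<1.90 mg/dL"). The calcium row does not show the ionized criterion.

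SAP Appendix A treats both outcomes as binary, compared between arms by a Wald test from a mixed model.

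**The concern.** Both numbers look like limits in mmol/L printed with mg/dL beside them. For calcium, the two criteria in one definition do not fit together once they are put in the same unit. Because the same units appear in five places across two documents, this is neither an isolated slip nor an effect of text extraction.

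The stake is the count. A limit set far below any value likely to be seen gives few or no events whatever the fluid removal strategy does. Protocol 11.4 names these disturbances as risks of the trial. Protocol 13.3.1 says events that make up the safety outcomes go into outcome reporting and are not reported again as adverse events, and Table 7 sends expected ones to the regular DSMB meetings. The adverse event list in 13.1 names the disturbances without a numeric limit, so the outcome definitions are the only place where a limit is given.

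**Working it through.** **Inputs.** Limits from protocol 4 and 5.8.3 and SAP 3.5.3, 5.2.2.5 and Table 3: potassium 3.0 mg/dL, total calcium 1.90 mg/dL, ionized calcium 0.90 mmol/L. Molar masses are physical constants, not taken from the documents: K 39.098 g/mol, Ca 40.078 g/mol. The documents give no expected event rate for these outcomes, so there is no design figure to reproduce.

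**Formula.** mmol/L = mg/dL × 10 / molar mass; mg/dL = mmol/L × molar mass / 10.

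**Potassium.**
- As printed: 3.0 × 10 / 39.098 = 0.77 mmol/L.
- Same number read as mmol/L: 3.0 × 39.098 / 10 = 11.73 mg/dL, which is 11.73 / 3.0 = 3.9 times the printed limit.

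**Calcium.**
- Total, as printed: 1.90 × 10 / 40.078 = 0.474 mmol/L.
- Ionized, as printed: 0.90 mmol/L = 0.90 × 40.078 / 10 = 3.61 mg/dL.
- Ratio of total limit to ionized limit: 0.474 / 0.90 = 0.53.
- Total, same number read as mmol/L: 1.90 × 40.078 / 10 = 7.61 mg/dL, which is 7.61 / 1.90 = 4.0 times the printed limit.

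These readings in mmol/L are conversions only. They do not establish what the authors intended.

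**What follows for calcium.** Ionized calcium cannot exceed total calcium in the same sample. A patient with total calcium below 0.474 mmol/L therefore also has ionized calcium below 0.90 mmol/L, so the total criterion identifies no case that the ionized criterion would not. A patient with only total calcium measured would need a value below 0.474 mmol/L to count.

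**Does the ionized criterion still yield events?** The protocol plans: "We will enroll 112 subjects or 56 patients per group". With an assumed patient-level event rate p on the ionized criterion, and patients treated as independent, expected events are 56p and the chance of at least one is 1 − (1 − p)^56:

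| Assumed p | Expected events in 56 | P(at least one) |
|---|---|---|
| 1% | 0.6 | 43% |
| 5% | 2.8 | 94% |
| 10% | 5.6 | 99.7% |
| 20% | 11.2 | >99.9% |

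The rates are illustrative. They show that the hypocalcemia outcome is not forced to zero under the written definition.

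**Table 3.** If a programmer worked from the row label instead of section 5.2.2.5, only the 0.474 mmol/L criterion would remain, and hypocalcemia would then behave like hypokalemia. With no events in either arm, the binary mixed model in Appendix A could not estimate a treatment effect.

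**The case against.** **The ionized criterion works.** A reader might infer that both outcomes are impossible and that both would report about zero in each arm. The documents do not support that for hypocalcemia. The second criterion has a coherent unit and stands in protocol 4 and 5.8.3 and SAP 3.5.3 and 5.2.2.5. Only the Table 3 label omits it, and a row label is not the definition. This objection stands in full.

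**Zero hypokalemia depends on programming.** The documents do not state the unit in which potassium is recorded and specify no conversion. An analyst may simply apply 3.0 to values in mmol/L or mEq/L. That would produce events, but under a definition that neither document states, and programmers could differ. The objection makes the result conditional; it does not remove the defect.

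**The stakes are limited.** A reader might also infer that the trial will wrongly declare both strategies free of these disturbances. No section plans such a conclusion: Table 3 tabulates patients, episodes and P values. Protocol 11.3 says the trial is not sized to show differences in adverse events, no interim analysis is planned, and 11.4 leaves electrolyte monitoring and replacement to ICU practice. Daily serum electrolytes (8.3.2) and laboratory data (Appendix F1) are recorded, so a corrected limit could be applied to stored values. This stands, and it lowers the severity. One gap remains: neither place says whether ionized as well as total calcium is captured.

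**Conclusion.** The unit defect is real. The potassium limit is 0.77 mmol/L with no alternative criterion. The total-calcium limit is 0.474 mmol/L, about half the ionized limit beside it.

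- **Hypokalemia:** about zero events in each arm if the unit is applied literally.
- **Hypocalcemia:** counted through ionized calcium only, so patients with only total calcium measured are missed. The size of the undercount depends on how often ionized calcium is measured, which the documents do not give. If that frequency differs between ICUs or over calendar time, the comparison could be biased, because in a stepped-wedge design the share of patients on the restrictive strategy rises with time.
- **Hypocalcemia at about zero:** only if the Table 3 label is programmed as printed.

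The calcium inconsistency follows from the documents' own figures, plus the fact that ionized calcium is a part of total calcium. For potassium the documents offer no internal comparison: that values below 0.77 mmol/L essentially never occur is general physiology, taken here as an assumption. The same assumption underlies the statement that the total-calcium criterion would essentially never be met.

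Severity is moderate. Two of 21 safety outcomes are affected in a feasibility trial whose primary outcomes are separation, adherence and recruitment, and the error can be corrected before analysis.

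**What to change.** Before the safety outcomes are programmed:

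1. The authors confirm the intended unit and value for potassium and for total calcium.
2. Make the same correction in protocol 4 and 5.8.3 and in SAP 3.5.3, 5.2.2.5 and Table 3, and check that the total and ionized calcium limits are consistent when put in one unit.
3. Restore the ionized criterion in the Table 3 row, or explain why it is left out.
4. State in SAP 5.2.2.5 the unit in which each laboratory value is recorded and any conversion applied, and say how a patient with only one of the two calcium measures is classified.

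The cost is wording in both documents. Sample size and visit schedule are untouched. The only possible extra work is on the data collection form, if ionized and total calcium are not already recorded separately with their units.

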### **Sample Size/Interim Monitoring**

[figure not shown]
1. Using the sample size calculation for SW-CRT design, 111 patients will have 80% power at a two-sided alpha of 0.05 to reject the null hypothesis that the average UFNET rate was at least 0.53 mL/kg/h different between the two groups, using intra-cluster correlation coefficient of 0.01, at a standard deviation of 0.75, and assuming mean UFNET rate of 1.0 mL/kg/h. We will enroll 112 subjects or 56 patients per group.
2. The principal analysis will be intent-to-treat based upon randomization assignment.
3. The trial progress will be evaluated by an independent Data and Safety Monitoring Board (DSMB). Being a feasibility study there will be no interim analyses.

## 5 TRIAL DESCRIPTION

### 5.1.1 BACKGROUND

Fluid overload is present in two-thirds of critically ill patients with AKI before initiation of KRT, and despite fluid removal, mortality ranges between 40% to 60%. Emerging evidence suggests that the  $UF_{NET}$  rate, a process of care variable, has a “J” shaped association with mortality (Figure 1). Slower  $UF_{NET}$  rates, compared with faster rates, increase exposure to fluid overload and organ edema. In contrast, faster rates compared with slower rates are associated with hemodynamic instability, hypotension and ischemic organ injury. Thus, both slower and faster rates are associated with mortality compared with moderate  $UF_{NET}$  rates in observational studies (Section 5.2). Thus, it is imperative to determine whether the  $UF_{NET}$  rate-mortality relationship is causal. By establishing the feasibility of the restrictive  $UF_{NET}$  rate group, this proposal will be the harbinger of a phase III trial to examine causal effects of  $UF_{NET}$  rate on patient-centered clinical outcomes.

[figure not shown]
**Figure 1: An emerging conceptual model of the association between  $UF_{NET}$  rate and mortality in critically ill patients.**

### 5.1.2 PATHOPHYSIOLOGIC CHANGES DURING $UF_{NET}$

As fluid is removed from the intravascular space during extracorporeal ultrafiltration, vascular refill occurs due to fluid shifting from the extravascular and interstitial spaces into the intravascular space. When the rate of fluid removal is higher than the rate of vascular refill, intravascular hypovolemia results in hypotension, decreased organ perfusion and ischemic injury. Although there are patient-related (e.g., comorbid conditions, reduced vasomotor tone) and other dialysis-related factors (e.g., reduced plasma osmolality due to solute clearance) that contribute to hemodynamic instability (Figure 2), several studies indicate that there is a direct relationship between higher  $UF_{NET}$  rate, a process of care variable, and subsequent risk of hypotension and mortality.

**Figure 2: Pathophysiology of hemodynamic instability during  $UF_{NET}$ .**

*HIRRT, Hemodynamic instability related to kidney replacement therapy; CKRT, Continuous kidney replacement therapy; SLED, Slow extended daily dialysis; HD, hemodialysis; KRT, Kidney replacement therapy*

### 5.1.3 ASSESSMENT OF INTRAVASCULAR VOLUME

Clinical assessment of intravascular volume is the holy grail of hemodynamic management in critically ill patients during ultrafiltration. Conventionally used hemodynamic parameters such as blood pressure, central venous pressure, pulmonary artery occlusion pressures are insensitive to early changes in intravascular volume. Although dynamic parameters such as pulse pressure variation, stroke volume variation, IVC collapsibility, passive leg raising are used to predict fluid responsiveness in critically ill patients, these technologies have several pitfalls.

First, assessing pulse pressure variation and stroke volume variation to predict fluid responsiveness require that the patient is mechanically ventilated, not on low tidal volume ventilation, sedated and not spontaneously breathing. Second, IVC collapsibility and passive leg raising tests are not feasible as they cannot be done continuously. Third, while these technologies have been validated for predicting fluid responsiveness in critically ill patients, its validity for predicting intradialytic hypotension during fluid removal in critically ill patients is unknown. Other technologies such as hematocrit monitoring and bioimpedance analysis used in outpatients undergoing hemodialysis have not been validated in critically ill patients for fluid removal. Thus, current assessment of intravascular volume during ultrafiltration is mostly clinical based on surrogate measures such as blood pressure, fluid balance, and physical examination of the patient (e.g., capillary refill).

### 5.1.4 CURRENT CLINICAL PRACTICE

Currently there is a wide variation in the clinical practice of  $UF_{NET}$ . Clinicians arbitrarily set  $UF_{NET}$  rates based on blood pressure and severity of FO and titrate  $UF_{NET}$  rate as tolerated by patient hemodynamics. However, blood pressure is insensitive to early changes in intravascular volume. Thus, hypotension can occur abruptly during fluid removal when intravascular hypovolemia occurs and is difficult to predict. Despite careful titration of  $UF_{NET}$

rate, hypotensive episodes complicate 19% to 97% of patients during CKRT, and intradialytic hypotension has been independently associated with three-fold increase in odds of death in critically ill patients.

## 5.2 PRELIMINARY WORK

[figure not shown]
### 5.2.1 HIGH UFNET RATES DURING CKRT ARE ASSOCIATED WITH MORTALITY AND KRT DEPENDENCE

Using the Randomized Evaluation of Normal versus Augmented Level (RENAL) of the Renal Replacement Therapy trial cohort, we examined the association of the UFNET rate with outcomes. Of 1,434 patients, the 90-day mortality among patients who received UFNET rate >1.75 vs. 1.01-1.75 vs. <1.01 mL/kg/h was: 48.6% vs. 39.2% vs. 44.9%; P=0.01, respectively. Using Gray model, UFNET rates >1.75 mL/kg/h compared with rates 1.01-1.75 mL/kg/h (adjusted HR range, 1.44-1.77, P=0.004) and rates <1.01 mL/kg/h (aHR range, 1.51-1.66; P=0.01) was associated with lower survival. Every 0.5 mL/kg/h increase in UFNET rate was associated with 7% increased odds of death (aOR, 1.07; 95%CI, 1.00-1.15; Figure 3). Using a joint model, longitudinal increase and variation in UFNET rates over time was also associated with risk of death ( $\beta=0.056$ ; P<0.001). UFNET rates of >1.75 mL/kg/h, were also associated with an increased risk of cardiac arrhythmias requiring treatment (36.8% vs. 30.8%; P=0.08).

After accounting for competing risk of death, UFNET rates >1.75 mL/kg/h compared with UFNET rates, 1.01-1.75 mL/kg/h (cause-specific aHR, 0.79, 95%CI, 0.66 – 0.95) and UFNET rates <1.01 mL/kg/h (aHR, 0.69, 95%CI, 0.56-0.85) was associated with lower renal recovery and longer dependence on KRT.

We also investigated whether the daily fluid balance was a mediator of the relationship between UFNET rate and mortality, with baseline day one fluid balance as moderator. We found that a more negative daily fluid balance attenuated the harmful mortality effect of high UFNET (>1.75 mL/kg/h) rate group compared with moderate (1.01-1.75 mL/kg/h) and low (<1.01 mL/kg/h) UFNET rate groups. However, despite this attenuation, the high UFNET rate (>1.75 mL/kg/h) group remained significantly and directly associated with higher mortality compared with the moderate UFNET rate group (average direct effect, 1.10, 95%CI, 1.04-1.16). These data add to the scientific premise and support the further need to conduct a randomized trial.

**Figure 3: In the RENAL cohort, a patient receiving a UFNET rate of 1 mL/kg/h had a 30.6% predicted risk of death and a patient receiving UFNET rate of 4.5 mL/kg/h had a 64.5% predicted risk of death.**

